### **WP2:8.3.3 Secondary Outcome Analysis: Multistate modelling of Patient level treatment modality history and mortality**

The results from the graphical Markov model will inform the development of a multi-state model,[66] for patients requiring renal replacement therapy. This will estimate the rates of: home and in-centre dialysis uptake, transplantation, transitions from one modality to another, and death (Fig. 2). The model will quantify the impact of changing centre patterns, identified by the graphical Markov model, on the rates of home dialysis usage. The transition rates will include random intercepts at the centre-

level to account for heterogeneity among dialysis units. The estimated parameters of this model will inform the health economic analysis (WP3).

*Figure 2. Multi-state model to estimate the rates of home dialysis usage combined, similar models will be built replacing home dialysis by two states for PD and HHD separately allowing transitions between these states*

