**5:WP2:** The survey will be sent to all 52 of the Dialysis Units in England. The survey data will be linked with the patient level routine data returns made from the 52 units to the UK Renal Registry. Linkage will be undertaken at Keele University.

**5:WP3:** Is all data driven. Research data will be obtained through Keele University and the UK Renal Registry under a data-sharing agreement.

**5:WP4:** The data synthesis, using aggregated data, will be undertaken by the research team in workshops held on University premises.

**5:WP5:** The intervention development will be co-designed with an Independent Reference group comprising patients, carers, health professionals and members of the national dialysis reference group. These workshops will be held on University Premises.

***In the following sections the protocol is ordered by WORK PACKAGE. Each paragraph is numbered first by the WP identifier, e.g. WP1: detail on rationale and design where needed, followed by the main section number and the appropriate subsection where relevant in the following order:***

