## **WP2:8 STATISTICS AND DATA ANALYSIS**

### ***WP2:8.1 Sample size calculation***

There is no formal sample size calculation for the national survey as this is not a sample, but a whole country study. The sample size is determined by the number of centres from which we obtain information through the survey, rather than the number of survey respondents per renal unit, which will determine the expertise with which it is completed and thus the accuracy of the information. With approximately 8 responses planned per renal unit, we would expect up to 400 completed surveys to be returned. The total number of patient-level observations is estimated to be around 27,000 and will depend on the number of patients on renal replacement therapy.

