The strength of this approach is that it provides a framework to identify potential causal relationships amongst many patient- and practice-related factors, and their impact on HD uptake, thereby offering a powerful tool to deal with the complexity likely to be identified by the ethnographic study. The main outcomes of this approach include (1) a causal graph that displays pathways of associations starting from demographic factors through intermediary factors, leading to home uptake, indicated by series of variables connected by arrows or lines, including a measure of relative importance – this will help present and greatly simplify the synthesis of findings (WP4); and (2) an interpretation based on graph theory and probabilistic theory to explore the relationship between selected subsets of variables and thus enable the assessment of competing hypotheses. This will provide a robust mechanism for the choice of the most important modifiable and cost-effective factors when developing the intervention (WP5).

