#### **WP2:8.5 Adjusted analysis**

The proposed models will examine the association between any two (or more) variables partitioning out the contribution of different groups of variables as relevant, led by group discussions (WP4). The rates of transitions from the multistate models will be adjusted for age and sex and include important centre-and patient-level explanatory variables.

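### The same 52 units identify the centre patterns and supply the estimated impact of changing them, so the projected benefit is likely to be inflated to the extent that the data do the selecting; the protocol states no correction

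*Protocol*

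**What the plan says.** Section 5 gives one set of centres for both exposure and outcome: "The survey will be sent to all 52 of the Dialysis Units in England", and "The survey data will be linked with the patient level routine data returns made from the 52 units to the UK Renal Registry".

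WP2:8.1 declines a power calculation: "There is no formal sample size calculation for the national survey as this is not a sample, but a whole country study". It also accepts that centres are the unit that counts: "The sample size is determined by the number of centres from which we obtain information through the survey".

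The results then pass through these steps:

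- WP2:8.3.2, on the graphical model: "This will provide a robust mechanism for the choice of the most important modifiable and cost-effective factors when developing the intervention".
- WP2:8.3.3, on the multistate model: "The model will quantify the impact of changing centre patterns, identified by the graphical Markov model, on the rates of home dialysis usage". Its parameters go to the health economic analysis.
- WP4 (Design and theoretical frameworks) uses the WP3 estimates to compare the factors on uptake, QALYs and costs.
- WP5:7.1 presents 6-10 factors that best explain centre variation, with modelled cost and QALY effects, and cuts them to 3-5 by consensus.

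On adjustment, WP2:8.5 says associations will be examined "partitioning out the contribution of different groups of variables as relevant, led by group discussions (WP4". The multistate rates are adjusted for age and sex plus important covariates that are not named. WP4 also plans re-analysis of WP1-3 data after its first workshop.

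**The concern.** If a factor enters the list partly because its association with uptake is large in these 52 units, its estimate in the same units carries the favourable chance error that got it chosen. Fitting a second model to the same centres does not remove that error, because no new centres enter. The whole-country argument does not remove it either. It would serve a description of the 52 units, but the estimates are used to project what changed practice would do.

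The other safeguards in the protocol address different problems. Centre-level random intercepts in WP2:8.3.3 handle clustering. WP3:8 plans sensitivity testing, which shows which inputs drive the result, and calibration to registry and published data. Neither asks whether the selected inputs are too large.

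The choice of intervention bundle and its projected cost-effectiveness and return on investment are at stake.

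**Working it through.** The protocol states no power, effect size or projected benefit for WP2, so there is no figure to reproduce. The check asks how many independent units lie behind a centre factor, and how much selecting and estimating on the same units could matter.

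**1. Effective sample size**

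- Inputs: 52 units (section 5); for patients, "The total number of patient-level observations is estimated to be around 27,000" (WP2:8.1); home therapy prevalence from 6% to 27% across centres (section 1.1).
- Patients per unit: 27,000 / 52 = 519.
- Between-centre SD, taking the range of about 50 normal values as 4.5 SD (assumption): (27 - 6) / 4.5 = 4.7 points.
- Within-unit standard error at the midpoint of 16.5% (assumption): sqrt(0.165 x 0.835 / 519) = 1.6 points.
- Share of observed between-centre variance due to patient sampling: (1.63 / 4.67)^2 = 0.12.

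Only about 12% of the spread is patient sampling. For centre-level factors the working sample is therefore about 52, and the 27,000 patients do little to help.

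**2. Selecting and estimating on the same 52 units**

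The simulation model for unit *i* was y_i = sum of b_k x_ik + e_i, with K standardised candidate factors and true joint R2 set in advance. The 6 or 10 strongest factors were kept and refitted by least squares on the same units, with 1,500 to 3,000 runs per scenario.

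Ratio = (sum of |estimated effects|) / (sum of true effects in the estimated directions), for a favourable change of 1 SD in each factor.

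The assumptions, none of them given in the protocol, were K = 12, 20, 30 or 40; R2 = 0.3, 0.5 or 0.7; and one third or all of the factors active. Each range below runs over K and over 6 or 10 factors kept.

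| Selection | Active factors | R2 = 0.3 | R2 = 0.5 | R2 = 0.7 |
|---|---|---|---|---|
| Strongest marginal association | one third | 1.63-2.35 | 1.30-1.57 | 1.13-1.34 |
| Forward selection | one third | 1.87-3.75 | 1.46-2.17 | 1.22-1.49 |
| Strongest marginal association | all | 1.47-2.61 | 1.18-1.77 | 1.06-1.41 |

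Overall the ratio is 1.06 to 3.75, and 1.18 to 2.17 at R2 = 0.5.

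**3. Comparators**

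- Factors and directions fixed in advance: 0.827 / 0.830 = 1.00.
- Selection on 26 units and estimation on the other 26: 1.00 to 1.02. The price is weaker factors: with K = 20 and 6 kept, the true benefit of the chosen set is 0.93, against 1.12 when all 52 units select (one third active, R2 = 0.5).
- No true effects at all, with forward selection of 6-10 factors: apparent R2 is 0.29-0.35 for K = 20, 0.36-0.45 for K = 30 and 0.40-0.52 for K = 40.

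**4. Limits**

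This is a centre-level stand-in for the planned ordered regressions and multistate model. The ratio combines two effects, choosing the factors from the data and taking their direction from the data, and does not separate them. It shows the direction of the bias and a plausible range, and does not forecast this study's result.

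**The case against.** **Selection is not by the data alone.** WP2:8.3.2 has the literature review and ethnography inform the choice and ordering of variables. WP5:7.1 draws the 6-10 factors from WP1 as well as WP2 and reaches 3-5 by consensus, with modifiability as a criterion. This stands, and it limits the bias: where these sources fix both factor and direction, the ratio is 1.00. It does not remove the bias, because the graphical model is still the stated selection mechanism.

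**A reader might infer a fixed inflation, such as three-fold.** Suppose 30 candidates, six real at r = 0.20, and the best eight kept. The ratio of mean absolute estimated to true correlation is then 3.1. Eight factors picked at random give 3.3 on the same measure. With 15 and 50 candidates the figures are 2.1 and 4.2 for selected factors, against 1.9 and 5.1 for random ones. That ratio therefore cannot be attributed to keeping the strongest factors, and it falls to 1.3-1.6 if the real correlations are 0.38. The documents support no single figure.

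**A reader might infer that WP4 discussion sets the adjustment for the multistate rates.** WP2:8.5 does not say so. The discussion wording concerns the association models; for the multistate rates, age and sex are fixed and the remaining covariates are simply not named. Nor does WP2:8.5 contradict WP2:8.3.2: one section governs the choice and order of variables, the other what is partitioned out.

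**The remedy may sit in a statistical analysis plan that was not available.** An optimism correction could be there, and its absence from the protocol is not itself a fault. What the protocol does fix is the sequence of selection, re-estimation and economic use, and the opening for discussion-led partitioning and later re-analysis.

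**The study is exploratory.** That is true, but its estimates go on to rank factors by cost and QALY gain.

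**Conclusion.** The concern holds in a limited form. The same 52 units identify the centre patterns and provide the estimated impact of changing them, and those estimates feed the economic ranking. As far as the data decide which factors and directions are kept, the projected benefit is likely to be inflated, and the protocol states no correction.

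The direction of the bias is well supported: it appeared in every data-driven scenario and disappeared when factors and directions were fixed beforehand. The size is not known. The range of 1.06 to 3.75, or 1.18 to 2.17 at true R2 = 0.5, rests on assumed numbers of candidates, shares of active factors and effect sizes, and the low end is nearly harmless. It would be too strong to say that the benefit is inflated by a known amount.

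A second, smaller point is confined to the association models. WP2:8.5 and the planned re-analysis in WP4 allow the choice of what is partitioned out to be made after results are seen.

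**What to change.** 1. Before the survey is linked to uptake, fix the candidate variables, their ordering and the main adjustment sets, including the covariates of the multistate model beyond age and sex. Label anything added in WP4 as exploratory.
2. Repeat selection and estimation together in a bootstrap that resamples centres, and report how often each factor is selected.
3. Pass shrunken or optimism-corrected effects, with their bootstrap distribution, to the multistate and economic models in place of the selected point estimates.

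Splitting the 52 units would also remove the bias, but it finds weaker factors, so resampling all the centres is preferable.

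The cost is wording in the protocol or analysis plan and computing time; no new data are needed. The projected gains and savings will be smaller and less certain, and the WP5 workshops should see them in that form.

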Despite this, use of home therapies has declined by 20% between 2011 and 2015. The first in-depth analysis of Renal Registry data [1] found significant variability in the prevalence of home therapies between centres (ranging from 6% to 27% of dialysis patients). This is largely driven by centre variation in the proportions initiating dialysis with PD, 6.3% to 49.7%, or HHD, 0.02% to 6.6%. These disparities are compounded by less home dialysis use in patients from BME and more socially deprived postcodes. 28% of IHD patients are from BME populations, compared to 22% of those using PD and 13% HHD. The proportions treated with PD in centres with high BME populations (>60% of patients on the programme) vary at least two-fold, with a similar discrepancy seen between the least and most deprived quintiles of deprivation across the board. [1] These disparities corroborate earlier research that also indicated that the variation in home dialysis use was largely explained by centre practices, especially reflecting physician preference for home therapies. [14] The Ontario project, developed to increase home therapy use in the Canadian state, identified many sequential barriers to PD with a wide variation between centres in the chances of these being surmounted, even after patients had elected and considered eligible for treatment at home. [15-17] Other explanations include commissioning levers offering financial reward, lack of individualised patient education and emotional support or the use of competing treatments such as transplantation or varied approaches to delivering CHD (such as minimal care facilities or the provision of overnight dialysis shifts). [18,19] These findings point to the culture around home therapies within a centre playing a large part in their uptake and successful use. Maintaining a high prevalent home therapy population also depends on a low technique failure rate. Variation in technique failure is also largely determined by centre characteristics, [20] with better outcomes in centres using home therapies in a higher proportion of patients. [21]

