## **5 STUDY SETTING (by Work Package)**

**5:WP1** Four case study sites selected from the 52 dialysis units in England. Selection of the four case study renal units involved two-stage purposive sampling and was undertaken prior to grant submission. Stage 1 involved assigning each renal unit in England that offers PD and/or home haemodialysis as treatment options for renal patients (n=52) to one of four categories based on a home therapies uptake taxonomy developed using UK Renal Registry data [43]. The four categories in the taxonomy are: i) high uptake of home therapies (top 15% nationally based on the proportion of renal patients at each unit treated using home therapies); ii) high uptake of home therapies amongst BME patients (top 15%); iii) renal units with home therapy uptake for all patients at rates around the national median (ten above the median and ten below); and iv) renal units with home therapy uptake for BME patients at rates around the national median (ten above the median and ten below). As it is important that case study sites have a large enough cohort of patients potentially eligible for participation in the ethnography, renal units with fewer than 50 total renal patients and/or fewer than 20 BME patients were excluded from consideration as part of the Stage 1 sampling process.

Sampling in Stage 1 produced a long-list of potentially eligible renal units within each of the four groups in the taxonomy. Stage 2 involved further sampling to select a single case study site from each group, ensuring a balanced selection based on: maximum geographical variation across England (North, Midlands, South, London); population density of a renal unit's catchment area (urban/rural); sociodemographic characteristics of a unit's patient population (less affluent/affluent/mixed); and ethnic diversity (high/low BME populations). In addition to these criteria, a flexible approach was used in selecting the four case study sites that balanced the need for maximum variation in unit characteristics and practice with practicalities such as sites' willingness to participate in the study and accounting for the potential influence of unit transplantation rate on home therapy uptake. As transplantation may have an impact on home therapy rates, both units that are or are not also transplant centres will be represented.

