#### ***WP2:8.3.2 Primary Outcome: graphical Markov modelling of factors that explain the variation in home dialysis uptake***

We will employ sequences of regressions [53-64] coupled with a causal graph to define a graphical Markov model that extends path analysis to formulate an explanatory model for home dialysis uptake. The model is formulated by ordering the variables in groups of primary outcomes (e.g. HD uptake), potential intermediary variables (e.g. dialysis unit practices, centre characteristics, policy and commissioning, patient comorbidities) and background variables (Fig 1). The model is developed by fitting ordered sequences of linear or logistic regression models and the strength of associations is

quantified through partial correlation coefficients, with variables located on the left taken as response variables to those located to the right of them in a postulated ordering. The choice and ordering of the variables will be informed by the literature review and the ethnographic study. The associations between two variables in the model can be direct or indirect; for example, a dialysis unit characteristic (e.g. whether it is also a transplant centre) may affect home dialysis use directly or indirectly due to a unit practice identified by the survey. Importantly, it is possible to assess interactions or whether any association holds in the same direction and at the same magnitude for different patient demographics, e.g. ethnicity or socio-economic status.

[figure not shown]

[figure not shown]
Figure 1: Example of postulated order of sequences of regressions model variables. Variables located on the right are regarded as explanatory to those located to their left. The associations between two variables in different boxes can be direct or indirect through intermediary variables. SES: Socio-economic status

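### No centre-level slope for ethnicity or deprivation is stated, so a practice-by-ethnicity or practice-by-deprivation effect would get too small a standard error if the gap varies between units

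*Protocol*

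**What the plan says.** The primary analysis (Protocol WP2:8.3.2) builds the graphical Markov model by "fitting ordered sequences of linear or logistic regression models". Unit practices and characteristics are intermediate variables and home uptake is the outcome. The section marks as important that "it is possible to assess interactions or whether any association holds in the same direction and at the same magnitude for different patient demographics", with ethnicity and socio-economic status as its examples. It states no centre term, random or fixed.

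For the multistate model (WP2:8.3.3) the text is "The transition rates will include random intercepts at the centre" "level to account for heterogeneity among dialysis units". WP2:8.5 adds that the rates will be "adjusted for age and sex and include important centre-and patient-level explanatory variables". Ethnicity and deprivation are not named there, and interactions are neither planned nor ruled out. The multistate model is meant to size the effect of changing the centre patterns found in the graphical model, and its parameters feed the economic model in WP3.

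Section 5 (WP1) classifies units by home uptake among BME patients separately from uptake overall, so the study treats a gap that differs between units as plausible.

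**The concern.** A practice is a property of the unit and ethnicity is a property of the patient. Whether a practice narrows or widens the ethnic gap is therefore a cross-level question: at most 52 unit-specific gaps bear on it. A centre intercept moves every patient in a unit by the same amount on the model scale. It absorbs differences in level, but not differences in the gap that the measured practices leave unexplained. If that residual variation exists and has no term in the model, the interaction is judged as though each BME patient were independent evidence about the practice. Its interval is then too narrow.

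Unequal access by ethnicity and deprivation is a stated reason for the study, and results from these models are carried to the WP4 and WP5 workshops. An interaction shown with too much precision could make an unrelated practice look relevant to the gap.

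**Working it through.** The plan has no figure to reproduce. WP2:8.1 gives no formal sample size calculation, and the protocol states no significance level, standard error or variance for the gap.

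**Inputs from the protocol**
- 52 units (WP2:6) and about 27,000 patient observations (WP2:8.1), so n = 27,000/52 ≈ 519 per unit.
- BME share q = 0.28, the in-centre haemodialysis figure in section 1.1.

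**Assumptions**
- Home uptake p = 0.20, inside the 6% to 27% range in section 1.1.
- A lower BME share, q = 0.15, as an alternative.
- A two-sided 5% test.
- Between-unit SD of the log gap, τ, from 0 to 0.5.

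**Formula.** The sampling variance of one unit's log odds ratio is v = 1/[n p(1−p) q(1−q)]. Without a centre slope the model uses v; the true variance is v + τ². The ratio of model to true standard error is r = √[v/(v + τ²)], and the false-positive rate is 2[1 − Φ(1.96 r)].

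**Numbers put in.** v = 1/(519.2 × 0.16 × 0.2016) = 1/16.75 = 0.0597. At τ = 0.3, r = √(0.0597/0.1497) = 0.63, and 2[1 − Φ(1.24)] ≈ 0.216.

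**Simulations with no true interaction.** Both give every unit its own level.
- A works on odds ratios: 52 units of 519, BME share with median 22%, mean log odds ratio −0.3, 1,500 data sets per setting.
- B works on event rates: unequal units averaging about 519, mean BME share 0.25, the practice present in 26 of 52 units, 3,000 data sets per setting.

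False-positive rates without a centre slope (– means not run):

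| τ | Formula, q = 0.28 | Formula, one third of patients, q = 0.15 | A | B |
|---|---|---|---|---|
| 0 | 5.0% | 5.0% | 5.1% | 4.9% |
| 0.1 | 7.0% | 5.4% | – | 7.8% |
| 0.2 | 12.9% | 6.7% | 11.5% | 16.8% |
| 0.3 | 21.6% | 8.8% | 21.9% | 29.3% |
| 0.4 | 30.7% | 11.7% | 28.4% | 40.1% |
| 0.5 | 38.9% | 15.3% | – | 48.4% |

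With the between-unit variation of the gap in the model, the rates are 4.2%, 4.3%, 5.4% and 5.7% in A (τ = 0, 0.2, 0.3, 0.4), and 3.9% to 5.7% in B over the whole range. The mean standard error in B rises from 0.075 to 0.078 at τ = 0, and from 0.074 to 0.115 at τ = 0.3.

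**What τ = 0.3 means.** Around a mean log odds ratio of −0.3, 95% of units have a BME odds ratio between exp(−0.3 − 0.588) = 0.41 and exp(−0.3 + 0.588) = 1.33.

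**Limits.** These are simplified versions of one uptake step, not the full multistate model. They represent a model with centre intercepts. The primary regressions as written have none, and that case was not calculated. Deprivation was not simulated.

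**The case against.** The strongest reply is that the faulted test is not planned in the model that has the random intercepts. WP2:8.3.3 promises transition rates and the impact of changing centre patterns. Interactions appear only in WP2:8.3.2, and there as something possible. WP2:8.4 plans no subgroup analyses. Saying that the rates will include intercepts does not exclude slopes, and the graphical results are still to shape the model. An analysis plan that is not shown may add slopes. All of this stands, and it makes the point conditional. It does not remove it: the protocol itself names a random structure and its purpose, and where it does raise interactions it states no allowance for centres.

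A reader might infer more than the documents support:
- *That the model forces an identical gap in every unit.* It does not. A practice-by-ethnicity term lets the gap differ by measured practice, so only the residual gap is held equal. A common effect on the log-rate scale also gives different absolute gaps when baselines differ.
- *That false equity targets will follow.* The protocol sets no equity target and no significance threshold for choosing factors. WP4 and WP5 weigh ethnography, economics, literature and stakeholder consensus together.
- *That section 1.1 shows a varying gap.* "The proportions treated with PD in centres with high BME populations" do differ at least two-fold, but that is variation in level between such centres, which an intercept captures. The separate ranking in section 5 makes a varying gap plausible without measuring it.

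It is also fair that τ is unknown, that nothing is lost at τ = 0, and that unit-specific slopes would be fragile where cells are sparse.

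**Conclusion.** The point holds in conditional form. As written, neither model provides a centre-level slope for ethnicity or deprivation. If the residual gap varies between units and a practice-by-ethnicity or practice-by-deprivation term is fitted, its standard error will be too small. For ethnicity at full size the inflation is already material at an assumed SD of 0.2. With far fewer patients and a lower BME share it is modest. The direction for deprivation follows from the same reasoning, but its size is not known. The SD of the gap is an assumption throughout; the study's own data can estimate it. This is an inexpensive improvement to the analysis and not evidence that any planned result is wrong.

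**What to change.** State in WP2:8.3.2, and in WP2:8.3.3 if such terms are carried into the home-uptake transition, that any model with a practice-by-ethnicity or practice-by-deprivation term will include a centre random intercept and a centre random slope for that patient factor. The interaction is then tested against the between-unit variation of the gap, and the estimated SD of the unit gaps is reported with its interval.

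Name the fallback in advance. If the slope model does not converge, estimate each unit's gap and regress the gaps on practice across units, with a between-unit variance component.

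Limit this to combined home uptake. Section 1.1 gives home haemodialysis initiation of 0.02% to 6.6% by centre. Even the top figure means about 519 × 0.066 ≈ 34 starters in an average-sized unit, too few to split by ethnicity.

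No new data are needed. The cost is a slope variance for each patient factor examined (two if both are) on one step, a centre intercept in the primary uptake regression, some risk of non-convergence, and wider interaction intervals if the gap does vary.
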